5.2 Schedule of Events

Procedure	Study Period	Screening Period	Treatment Period								Safety Follow-up Period		
			Up to 72 hours	0 (Pre-dose)	0.5 (Post-dose) ^b	4 ± 1	7 ± 1	14 ±2	21 ±2	28 ±2	42 ±2	56 ±2	84 ±2 or ET
Consent		X											
Eligibility criteria review		X	X										
Demographics ^c		X											
Medical/surgical histories		X											
Vital signs ^d		X	X	X	X	X	X	X	X	X	X		X
Physical examination ^e		X	X	X	X	X	X	X	X	X	X		X
Concomitant medications		X	X	X	X	X	X	X	X	X	X		X
AE Assessment		X	X	X	X	X	X	X	X	X	X		X
12-lead ECG		X		X					X				X
Efficacy assessments ^f		X		X	X	X	X	X	X	X	X		X
Chest imaging ^g		X	X	X			X	X	X	X	X		X
Ventilation Parameters ^h			X	X	X	X	X	X	X				
Randomization (IWRS, Part 2 only)				X									
Investigational Product administration				X									
Local Labs													
Hematology		X	X	X	X	X	X	X	X	X	X		X
Serology ⁱ		X											
Serum chemistry		X	X	X	X	X	X	X	X	X	X		X
High sensitivity troponin		X	X	X	X	X	X	X	X	X	X		X
d-dimer		X	X	X	X	X	X	X	X	X	X		X
Acute phase reactants (ferritin, CRP)		X	X	X	X	X	X	X	X	X	X		X

UCSF	Clinical Study Protocol No. UCSF-cePolyTregs-01	Page 18 of 72
------	---	---------------

Study Period	Screening Period	Treatment Period								Safety Follow-up Period		
		Study Day ^a										
Procedure	Up to 72 hours	0 (Pre-dose)	0.5 (Post-dose) ^b	4 ± 1	7 ± 1	14 ± 2	21 ± 2	28 ± 2	42 ± 2	56 ± 2	84 ± 2 or ET	
Urinalysis	X	X	X	X	X	X	X	X	X	X	X	
Pregnancy test (urine) ^j	X								X	X	X	
Mechanistic Collections												
Endotracheal Aspirate ^k		X	X	X	X	X	X	X				
Mini BAL ^{k,l}		X	X	X	X	X	X	X				
Whole blood		X	X	X	X	X	X	X		X	X	
Urine		X	X	X	X	X	X	X				

Abbreviations: AEs = adverse events; CRP = C-reactive protein; D = Day(s); ECG = electrocardiogram; ET = early termination; HBsAg = hepatitis B virus surface antigen; HCV = hepatitis C virus; HIV = human immunodeficiency virus; IP = investigational product; IWRS = Interactive Web Response System; min = minute(s); PD = pharmacodynamic.

^a Safety (e.g., AE assessments, vital signs, physical examinations) and efficacy assessments will be performed daily during the period in which subjects remain hospitalized.

^b Assessments should be measured at 12 hours (± 6 hours) post dose.

^c Includes subject's sex, age, race, and ethnicity.

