^d Vital signs include systolic and diastolic blood pressure, pulse, respiration rate, SpO₂ (oxygen saturation via pulse oximeter) and temperature (includes height and weight at the Screening Visit). Vital signs (except for temperature and weight) will be monitored periodically for a minimum of 30 minutes after administration of IP or placebo. Subject must be seated or in a semi-recumbent position in a rested, calm state for at least 3 minutes before vital signs are collected.

^e Physical examination will be *complete* at Screening and *targeted* for all other study days. At a minimum, the *complete physical examination* should include assessments of the skin, head and neck, lungs, cardiovascular system, abdomen, and extremities. A *targeted physical examination* will include assessment of any new subject complaints or changes from baseline.

^f WHO severity scale for COVID-19 pulmonary syndrome, Sequential Organ Failure Score; efficacy will be assessed in both Parts 1 and 2 of the study.

^g Radiograph or CT imaging should be performed as scheduled to the extent possible and should be included as study data regardless of time of collection; missed scans will not be considered a protocol deviation. Subjects who are ambulatory and discharged from hospital may forego further imaging if impracticable without incurring a protocol deviation.

^h Mode of ventilation, FiO₂, SpO₂, plateau pressure, peak pressure, PEEP collected daily per local procedure.

ⁱ Serology includes HBsAg, anti-HCV Ab, anti-HIV Ab (if positive, HCV RNA will be measured).

^j Pregnancy testing should be conducted at screening and all visits after hospital discharge.

^k Samples will be collected until the removal of the endotracheal tubes, with the last sample collection at the time of removal.

^l Mini BAL collections are at PI discretion based on exclusion criteria. Mini BAL **exclusion criteria**: FIO₂ > 0.8, PEEP > 14 cm H₂O, hemodynamic instability despite fluid and vasopressor support, open external ventricular device or intracranial pressure greater than 15 mmHg, INR greater than 2.0 within 36 hours of mini BAL, platelets <50 × 10³/mm³ within 36 h of mini BAL (Hendrickson 2017). Missed collections will not be considered protocol deviations.

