11.8 Mechanical Ventilation Status

If the patient is receiving invasive mechanical ventilation, ventilatory parameters will be collected daily between 06:00 and 10:00, including the following, per local procedure:

Mode of ventilation, FiO₂(Fraction of inspired oxygen), SpO₂ , plateau pressure, peak pressure, PEEP (Positive End-Expiratory Pressure). If an ABG (arterial blood gas) is obtained during that time, then the PaO₂ (Partial pressure of arterial oxygen) will also be collected.

If the patient is receiving non-invasive ventilation, the level of inspiratory pressure, FIO₂, and PEEP will be registered. If the patient is receiving high-flow oxygen, the flow rate and the FIO₂ will be recorded.

The proportion of subjects requiring mechanical ventilation will be assessed on Study Days 7, 14, 21, and 28, and the number of days free of mechanical ventilation will be assessed on Days 28 and 56.

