12 ADVERSE EVENTS

An AE is defined as any unfavorable and unintended sign (including an abnormal laboratory finding), symptom, or disease or any worsening of a pre-existing condition temporally associated with the use of a study drug, whether or not related to study drug. From signing the ICF to study drug administration, all SAEs and nonserious AEs related to protocol-mandated procedures will be recorded on the SAE/AE eCRF. All other untoward medical occurrences observed during screening, including exacerbation or changes in the medical and surgical history will be captured on the medical and surgical history eCRF.

An AE that occurs before the first administration of the study drug will be considered a pre-treatment AE. A TEAE is defined as any adverse event that was not present before the first administration of the study drug, or any event already present, that worsens in either severity or frequency, following exposure to the study drug. AEs that occur after treatment with IP or during the Safety Follow-up Period will be documented on the AE eCRF. The investigator will assess AE severity, the causality relationship of the AE to study drug, and will treat the subject as medically required to ensure the subject's safety.

AEs will be captured through the EOS Visit at Day 56 or the ET Visit. Reportable adverse events are defined based on timing of study drug administration, as follows:

- Treatment – Day 7: AEs grade 3+ that are not expected to occur in critically ill patients, per the discretion of the investigator.
- Treatment Day 8 – Day84/EOT: AEs grade 4+ that are not expected to occur in critically ill patients, per the discretion of the investigator.

Events expected in the critically ill and are being captured in the eCRF should not be reported as adverse events unless considered to be related to the study drug or unexpectedly severe or frequent per the discretion of the investigator. These include but are not limited to; need for vasoactive drugs or fluids for hypotension, decreased PaO₂/FiO₂, transient hypoxemia, need for renal replacement therapy, or worsening acute respiratory distress syndrome.

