12.2 Adverse Events of Special Interest

To date, there have been no clinical studies using cePolyTregs, and nonclinical studies with autologous, homologous products have not demonstrated specific toxicities related to administration of adoptively transferred Tregs. Potential adverse events of interest in the COVID-19 setting based on the biology of cePolyTregs include infusion/hypersensitivity reactions and infections including pneumonia and those involving pathogens not anticipated in a COVID-19 setting; these clinical parameters will be closely monitored in the current study.

The following events are defined as AESIs that should be reported by completing the Adverse Event eCRF and AESI eCRFs within 24 hours of the site's awareness of them, even if they do not meet criteria for an SAE:

- Evidence of hypersensitivity or transfusion incompatibility (e.g. new rash, urticaria, new onset bronchospasm).
- Diagnostically or clinically confirmed respiratory infections that were not present before study drug infusion AND that require a treatment course with antimicrobial agents, operative management, or procedural drainage.
- Within 6 hours of IP exposure:
 - New ventricular tachycardia, ventricular fibrillation, or asystole or any cardiac arrhythmia requiring cardioversion.
 - Hypoxemia requiring an increase in FiO₂ of 0.2 or more and/or an increase in PEEP of 5 cm H₂O or more to maintain SpO₂ in the target range of 88–95%, for a sustained duration (>2 hours) and not associated with a care procedure.

- Pulmonary Embolism

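### Above a pre-infusion FiO2 of 0.8 the hypoxemia AESI can be triggered only through PEEP, and no dose-timed ventilator reading falls within its 6-hour window except at hour 6

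*Combined protocol and SAP*

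**What the plan says.** Section 12.2 lists this event: "Hypoxemia requiring an increase in FiO₂ of 0.2 or more and/or an increase in PEEP of 5 cm H₂O or more". It applies "Within 6 hours of IP exposure". The increase must be needed to keep SpO2 at 88–95%, and it must hold "for a sustained duration (>2 hours) and not associated with a care procedure". Sites report AESIs "within 24 hours of the site's awareness of them, even if they do not meet criteria for an SAE".

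Other parts of the protocol bear on it:

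- **Eligibility (9.1, 9.2).** Entry requires PaO2/FiO2 below 300 and PEEP above 5. There is no upper limit on FiO2. Footnote l of the Schedule of Events (5.2) says "Mini BAL collections are at PI discretion based on exclusion criteria", and those criteria include FiO2 above 0.8. Such a value bars the sample, not the subject.
- **Ventilator data.** The Schedule marks ventilation parameters pre-dose on Day 0 and at Day 0.5, where footnote b says "Assessments should be measured at 12 hours (± 6 hours) post dose". Section 11.8 adds that "ventilatory parameters will be collected daily between 06:00 and 10:00".
- **General AE reporting (12).** Events expected in the critically ill, including decreased PaO2/FiO2, transient hypoxemia and worsening ARDS, "should not be reported as adverse events unless considered to be related to the study drug or unexpectedly severe or frequent", as the investigator judges.
- **Other capture after dosing.** Sections 10.4 and 10.5 require vital signs, including SpO2, for at least 30 minutes after infusion and then until they settle. Section 11.14 lists a change in oxygen or ventilator among the items to record after dosing.

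**The concern.** Hypoxemia soon after an intravenous cell infusion is a safety signal this trial needs to see. Section 12.2 states that the product has had no clinical studies. Part 1 can escalate after as few as 3 subjects (8.7), and AESI frequency is a secondary safety endpoint in both parts (8.6.2).

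The definition measures worsening as an absolute rise in a setting that has a ceiling. The closer a subject is to that ceiling before infusion, the less room there is to register worsening, so the AESI count is least sensitive in the subjects with the least reserve. If the eCRF holds no FiO2 and PEEP values for the hours in question, nobody can later check whether the criterion was met. In Part 2 this matters further because site staff other than investigators are unblinded (10.2, 10.7) and capture starts with the site noticing the event.

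**Working it through.** The plan states no computed figure on this point, so there is nothing to reproduce. The inputs are the two limbs, the window and the duration (12.2), FiO2 expressed as a fraction (section 6), the entry criteria (9.1, 9.2), and the reading times (5.2, 11.8).

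**1. Room for an FiO2 rise.** Largest possible rise = 1.0 − pre-infusion FiO2.

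| Pre-infusion FiO2 | Largest rise | Rise of 0.2 possible? |
|---|---|---|
| 0.70 | 0.30 | yes |
| 0.80 | 0.20 | yes, just |
| 0.85 | 0.15 | no |
| 0.90 | 0.10 | no |
| 1.00 | 0 | no |

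The FiO2 limb is unreachable for every value strictly above 0.80.

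**2. What remains above 0.80.** The PEEP limb does not depend on FiO2 and stays available. The uncounted case is a sustained worsening handled with a PEEP rise under 5. For example, a move from 0.85 to 1.0 is a rise of 0.15, which is below 0.2. A second gap is one of wording. The increase must serve to keep SpO2 at 88–95%, so it is unclear whether a subject who stays below 88% at FiO2 1.0 qualifies.

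**3. Dose-timed reading.** 12 − 6 = 6 hours and 12 + 6 = 18 hours. The Day 0.5 window therefore runs from hour 6 to hour 18 and meets the 0–6 hour AESI window only at hour 6.

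**4. Daily reading.** Let T be the infusion time and R the reading time, with R uniform over 06:00–10:00. The reading falls in the window if (R − T) modulo 24 is at most 6 hours. The documents give no infusion times, so these are assumptions:

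| Infusion time (uniform over) | Chance that the daily reading falls within 6 h after infusion |
|---|---|
| 24 hours | 6/24 = 25% |
| 08:00–18:00 | 5% |
| 10:00–18:00 | 0% |
| 06:00–10:00 | 50% |
| 00:00–06:00 | 67% |

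For 08:00–18:00, the chance that T falls before 10:00 is 2/10. Given that, the chance that R comes after T averages 1/4, and 0.2 × 0.25 = 0.05.

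**5. Duration.** The criterion needs more than 2 hours. One reading cannot show that, and the guaranteed SpO2 monitoring of 30 minutes is shorter.

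**The case against.** The best reply is that this is a narrow drafting gap in a well-watched setting. Several stronger readings are tempting, and the documents do not support them.

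- **That the AESI cannot occur above FiO2 0.8.** It can. The limbs are joined by and/or, and a PEEP rise of 5 or more is enough at any FiO2.
- **That no ventilator reading is scheduled in the window.** This is not strictly so. Day 0.5 opens at hour 6, the daily reading can fall inside, and an event that starts late and lasts more than 2 hours may still be present at the Day 0.5 reading.
- **That events will therefore be missed.** AESI reporting starts from the site's awareness, not from scheduled readings, and these are ventilated inpatients. SpO2 is followed until stable (10.4, 10.5), and a ventilator change is recordable (11.14).
- **That the AESI is the only capture.** Section 12 still admits events judged related or unexpectedly severe or frequent, and relatedness needs only some possibility (12.5). In Part 1 a related grade 3 or higher event that is also a shift of at least one grade is a DLT (8.8.3). Life-threatening events are SAEs (12.1), reportable whatever their cause (12.6.2).
- **That partial unblinding biases the assessment.** The investigators, who judge severity and causality, are blinded.

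All of this stands, and it turns the point from one of detection to one of definition and verification. It does not remove the point. The other routes rest on judgment, and the AESI is the only trigger for post-infusion hypoxemia that the protocol sets in numbers. Section 11.14 gives no threshold, timing or FiO2 and PEEP fields for its ventilator item.

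**Conclusion.** The point holds in a limited form. One of the two AESI limbs cannot be met above a pre-infusion FiO2 of 0.8, eligible subjects can be in that range, and a sustained worsening there with a PEEP rise under 5 is not counted. The status of a subject below the SpO2 range at FiO2 1.0 is unclear. Scheduled eCRF data cannot verify the AESI, because the dose-timed reading touches the window only at hour 6 and the daily reading falls there by chance (0% to 67% under the assumed infusion times).

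The arithmetic on FiO2 needs no assumption. How many subjects it affects is not known from the documents. A reader might assume a share: 10–30% above 0.8 would be 5–15 of 50 treated subjects in Part 2. No passage supports that range, and it would count subjects with high FiO2, not missed events. Footnote l shows that such values are foreseen, not how common they are at infusion. The change is worth making because it is cheap and the AESI count is otherwise least sensitive in the sickest subjects.

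**What to change.** Both changes concern reporting and data collection only. No care changes.

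1. **Section 12.2.** For subjects with pre-infusion FiO2 above 0.8, add a limb that counts a worsening from the pre-infusion state within the same 6 hours, sustained for more than 2 hours and not tied to a care procedure. The worsening is either an increase to FiO2 1.0, or SpO2 newly below the protocol's own 88–95% range at FiO2 1.0. The first part covers the move from 0.85 to 1.0 with SpO2 held in range. The word newly keeps out a subject who was already below range at FiO2 1.0 before infusion.
2. **Schedule of Events.** Transcribe FiO2, PEEP and SpO2 from the ICU flowsheet just before infusion and through 6 hours, for all Part 1 subjects and both arms of Part 2. A change that starts after hour 4 (6 − 2) cannot complete 2 hours by hour 6, so follow any change still open then until its duration is known. The AESI can then be checked against recorded values in the same way in each arm.

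The cost is one clause and one short eCRF page of values that an ICU already charts, and possibly a few more AESI reports.

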12.3 Clinical Laboratory Adverse Events

The investigator is responsible for reviewing the results of all laboratory tests as they become available and determining whether an abnormal value in an individual subject is a clinically significant change from the subject's baseline value(s). The investigator may repeat the laboratory test or request additional tests to verify the results of the original laboratory tests. In general, abnormal laboratory findings without clinical significance (based on the investigator's judgment) are not to be recorded as AEs. Laboratory values that are outside the laboratory reference range should be reported as AEs only if considered by the investigator to be clinically significant. Laboratory value changes that require treatment or adjustment in current therapy are to be considered AEs. When applicable, clinical sequelae (not the laboratory abnormality) are to be recorded as the AE.

12.4 Severity

All AEs, both serious and nonserious, will be assessed for severity using the NCI CTCAE v 5.0. The CTCAE scale includes unique clinical descriptions of AEs categorized by anatomy and/or pathophysiology. Reference the following website:

https://ctep.cancer.gov/protocolDevelopment/electronic_applications/docs/CTCAE_v5_Quick_Reference_8.5x11.pdf

The CTCAE scale displays Grades 1 through 5 with unique clinical descriptions of severity for each AE (including abnormal laboratory values), based on this general guideline provided in the scale. For AEs not covered by CTCAE, the conventional definition of severity will be used, as follows:

- Grade 1 (mild) AE: Minor; no specific medical intervention; marginal clinical relevance.
- Grade 2 (moderate) AE: Minimal intervention; local intervention; noninvasive intervention.
- Grade 3 (severe) AE: Significant symptoms requiring hospitalization or invasive intervention.
- Grade 4 (life-threatening or disabling) AE: Complicated by acute, life-threatening complications; need for intensive care or emergent invasive procedure.
- Grade 5: Fatal AE

12.5 Causality Assessment

The investigator or qualified sub-investigator is responsible for assessing and assigning the causality relationship of the event to study drug or study-related procedures (e.g., invasive

UCSF	Clinical Study Protocol No. UCSF-cePolyTregs-01	Page 54 of 72
------	---	---------------

procedures, such as venipuncture) using clinical judgment and the following categories of relatedness:

- Related: There is at least some possibility that the AE could be related to study medication administration.
- Not related: There is a high degree of certainty that the AE is NOT related to study medication administration.

In making a causality assessment of an AE, it should be considered as to whether or not the AE is expected to occur due to the underlying disease, based on the investigator's clinical experience.

12.6 Reporting Adverse Events

12.6.1 Reporting Procedures for Nonserious Adverse Events

The investigator is responsible for ensuring that all reportable AEs observed by the investigator or designee or reported by the subject are reported using the AE eCRF.

The investigator will assign the following AE attributes:

- AE diagnosis or syndrome(s), if known (if not known, signs or symptoms)
- Dates of onset and resolution (if resolved)
- Severity
- Causality relationship to study drug or study-related procedures
- Action taken
- Outcome

Follow-up of nonserious AEs will continue through the last day on the study and/or until a definitive outcome (e.g., resolved, resolved with sequelae, lost to follow-up) is achieved.

When a subject is withdrawn from the study because of a nonserious AE, the Sponsor and/or designee must be notified by email or phone within 48 hours.

12.6.2 Reporting Procedures for Serious Adverse Events

All SAEs, regardless of cause(s) or causal relationship to study drug, must be reported within 24 hours to the study Sponsor and/or designee. The investigator is responsible for ensuring that all SAEs observed by the investigator or reported by the subject are promptly assessed and reported to the Sponsor and/or designee. The investigator must assess the causality relationship of the SAE to study drug or any study-related procedure.

The procedures for reporting SAEs are as follows:

UCSF	Clinical Study Protocol No. UCSF-cePolyTregs-01	Page 55 of 72
------	---	---------------

- Within 24 hours of the investigator's knowledge of the event, enter data into the AE/SAE eCRF. If the electronic data capture system (EDC) is not available, the paper SAE Report Form may be used, but all data must be entered into the EDC once the EDC is available.
- Additional contact numbers and AE/SAE reporting instructions will be provided in the eCRF Completion Guidelines.
- For fatal or life-threatening events and all SAEs, also email and/or fax redacted copies of hospital records, autopsy reports, and other documents, when requested and applicable. Transmission of such documents should occur with personal subject details de-identified (redacted), without losing the traceability of a document to the subject identifiers. Entry of the initial report of the event into EDC should not be delayed in order to include these additional documents.
- The Sponsor and/or designee may request additional information from the investigator to ensure the timely completion of accurate safety reports.

The investigator must take all necessary therapeutic measures for resolution of the SAE. Any medications or therapies necessary for treatment of the SAE must be recorded in the event description section of the SAE form and the concomitant medication eCRF.

Follow-up of SAEs will continue through the last day on the study and/or until a definitive outcome (e.g., resolved, resolved with sequelae, lost to follow-up, fatal) is achieved.

While pregnancy is not considered an AE, all cases of fetal drug exposure via a maternal parent as study subject or pregnancy of a partner of a male study subject will be reported immediately to the Sponsor or its designee. Information related to the pregnancy must be documented on a Pregnancy Confirmation and Outcome Form, provided by the Sponsor or its designee, and the pregnancy should be followed until a definitive outcome has been determined.

The Sponsor or its designee will report SAEs as required to regulatory authorities and investigators in compliance with all reporting requirements, according to local regulations and ICH Good Clinical Practice (GCP).

The investigator will notify the appropriate Institutional Review Board (IRB) of SAEs occurring at the study site and other AE reports received from the Sponsor, in accordance with local requirements. The investigator or designee at each study site is responsible for submitting safety reports (initial and follow-up) and other safety information (e.g., in the revised cePolyTregs Investigator's Brochure) to the IRB and/or other applicable regulatory authorities and for retaining a copy in the study files.

